## 8.2.6 SADE potential

Each DD that did not lead to an AE/SAE should be assessed by the Investigator for its Serious Device Effect (SADE) potential as defined in Section 8.1.3.

DDs that lead to an AE/SAE will be recorded on the adverse event form as well.

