# 3.4 Endpoints

#### 3.4.1 Primary Endpoint

The following parameter will be measured as primary endpoint:

- Bone level change 12 months after implant loading.
- Occurrence of adverse device effects and device deficiencies that could have led to a serious adverse device effect

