## 8.1.3 Device Deficiency (DD)

A DD is an inadequacy of a medical device with respect to its identity, quality, durability, reliability, safety or performance. DD include malfunctions, use errors and inadequate labeling.

DDs that did not lead to an AE/SAE but could have led to an SAE if:

- suitable action had not been taken, or
- intervention had not been made, or
- circumstances had been less fortunate.

(DDs with SADE potential) are reported as specified for serious adverse events (SAEs/SADEs) in Section 8.3.1. Device Deficiencies will be classified into:

- DDs with Serious Adverse Device Effect (SADE) potential
- DDs without SADE potential

Device Deficiencies will be collected as described in Section 7.3.13. DDs that lead to an AE/SAE will be recorded on the adverse event form as well.

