# 8.1.4 Adverse Device Effect (ADE)

An ADE is an AE related to the use of an investigational medical device. This definition includes AEs resulting from insufficient or inadequate instruction for use, deployment, implantation, installation, or operation, or any malfunction of the investigational medical device. This definition includes any event resulting from use error or from intentional misuse of the investigational medical device. Any AE which has even a possible relationship to the investigational device will be classified as an ADE.

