#### 8.2 Assessment of Adverse Events and Device Deficiencies

Each AE should be assessed by the Investigator or another suitably qualified clinician who is trained in recording and reporting AEs and has been delegated to this role (such delegation must be captured in the Site Signature and Delegation of Authority Log) for seriousness, relationship to the investigational device or the procedure and severity as described in this chapter. A rationale shall be provided (short narrative) for each assessment.

Sponsor will review the investigator's assessment of:

- all adverse events and determine and document in writing their seriousness and relationship to the investigational device and procedure
- all device deficiencies and determine and document in writing whether they could have led to a serious adverse device effect

In case of disagreement between the sponsor and the principal investigator(s), both opinions will be communicated to concerned parties. The sponsor will evaluate the AEs for expectedness as described in Section 8.2.7

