# 8.2.2 Relationship to the investigational device

The Investigator should assess the relationship of the AE to the investigational device. In this study only the study implants (study control and study test implant) need to fulfil the protocol requirements, thus the relationship will be assessed to the study implant (=investigational device). Consequently, **AE's at implant positions of study implants** need to be assessed for relationship to the investigational device (study implant).

The relationship should be assessed using the following categories:

• Related – there is a reasonable causal and temporal relationship between the treatment with the investigational device and the AE.

- Possibly related or unknown The relationship between the treatment with the
  investigational device and the adverse event is less likely; however, the determination that
  there is no relationship cannot be made or is unknown.
- Not related no relationship between treatment with the investigational device and the AE is obvious.

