#### 8.3.2 Device Deficiency Reporting

DDs without SADE potential should be reported by the investigator to the sponsor within 30 days of awareness of the event using the Device Deficiency Form.

[figure not shown]
DDs with SADE potential shall be reported the same way as SAEs (see previous paragraph).

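### Sections 8.1.3 and 8.2.6 limit SADE potential to deficiencies that caused no adverse event, while section 8.2 covers all deficiencies, so the site's 24-hour route can be missed

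*Combined protocol and SAP*

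**What the plan says.** The second co-primary endpoint (section 3.4.1) has two components: "Occurrence of adverse device effects and device deficiencies that could have led to a serious adverse device effect". Three places then decide which DDs belong to the second component.

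- Section 8.1.3 describes the DDs that have SADE potential as "DDs that did not lead to an AE/SAE but could have led to an SAE if" one of three conditions is met. It goes on: "Device Deficiencies will be classified into" two groups, with and without SADE potential.
- Section 8.2.6 gives the site its task: "Each DD that did not lead to an AE/SAE should be assessed by the Investigator". A DD that did lead to an event is also to be entered on the adverse event form.
- Section 8.2 gives the sponsor a wider task, the review of "all device deficiencies and determine and document in writing whether they could have led to a serious adverse device effect".

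The reporting limit follows from the classification. Section 8.3.2 states: "DDs with SADE potential shall be reported the same way as SAEs", which under section 8.3.1 means 24 hours from awareness. DDs without SADE potential (8.3.2) and non-serious AEs (8.3.1) both have 30 days.

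**The concern.** The site and the sponsor work to different scopes for a classification that defines part of a co-primary endpoint and also sets the reporting clock. The DDs left out of the site's assessment are those that already caused some harm, and a near-miss with minor harm is at least as informative as one without.

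Two things are at stake. The first is timing. Whether the sponsor hears within a day depends on how the site classifies the DD when it becomes aware of it, and for this group the site is not asked to classify. The second is consistency of the endpoint. If the sponsor finds SADE potential in a DD that section 8.1.3 defines as having none, the plan does not say which of the two governs the co-primary listing.

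**Working it through.** No statistical figure is involved. The check follows one type of DD through the rules: it led to an AE that was not serious, but it could have led to a serious one. A DD that led to an SAE is not affected, because the SAE itself triggers the 24-hour route.

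**Step 1: classification at the site.** Under 8.2.6 the site does not assess this DD. Under 8.1.3 it cannot meet the description of a DD with SADE potential, because it led to an AE. Of the two groups in 8.1.3, only the one without SADE potential remains. The sentence that introduces the two groups states no exception for DDs with an AE, so a site could read it as covering them. The description just before it points the other way.

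**Step 2: reporting limit.**

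| Route | Site to sponsor | Sponsor to ethics committee | Latest total |
|---|---|---|---|
| DD with SADE potential, handled as an SAE (8.3.1, 8.3.2) | 24 hours | 7 days from awareness | 1 + 7 = 8 days |
| Same DD left unassessed under 8.2.6, non-serious AE (8.3.1, 8.3.2) | 30 days | 7 days, if the sponsor then finds SADE potential | 30 + 7 = 37 days |

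The second row assumes that the sponsor reclassifies on receipt and that its 7 days start then. The sponsor's review under 8.2 comes after the site's report, so it cannot recover the first 30 days. These are upper limits. Section 11.5.4 asks for data entry within 5 working days of a visit, which would shorten the delay for an event recorded at a visit.

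**Step 3: entry into the co-primary endpoint.**

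- *Study implant.* Section 8.1.4 makes an AE resulting from "any malfunction of the investigational medical device" an adverse device effect (ADE), and a possible relationship is enough, whatever the severity. The event therefore counts in the first component. At most it lacks the label of a DD with SADE potential.
- *Instruments and prosthetic parts.* Section 7.3.13 records DDs for every Straumann product used, but under section 8.2.2 "the relationship will be assessed to the study implant (=investigational device"). Section 8.2.3 adds the relationship to procedures belonging to study implant treatment, and the heading of Table 4 places procedure-related events with ADEs, whereas 8.1.4 refers to the device only. Depending on which governs, the AE may or may not be an ADE.
- *Non-study implants.* Several test or control implants may be placed in a study quadrant, and only the most mesial qualifying one is the study implant (3.3). An AE from a deficiency of another one generally falls outside both relatedness assessments (8.2.2, 8.2.3). Yet the hypothesis concerns the safety of SLActive implants (2.1), and the safety population is defined by receipt of any BLT Roxolid implant (9.3).

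For the last group, and possibly the second, the case enters the endpoint only if the sponsor's determination under 8.2 overrides the definition in 8.1.3.

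**The case against.** The strongest reply is that the sponsor already covers the endpoint. Section 8.2 requires a written determination for every DD, and nothing limits the endpoint to the site's classification. For the study implant no event is lost, because the resulting AE is an ADE. For instruments, the wording of Table 4 and the instruction in 7.2.3 to report treatment complications as an AE or ADE could bring the event in. Section 7.2.3 also makes missing primary stability of any implant an ADE, so the label is not strictly confined to study implants. Nothing disappears from the report either: section 9.2 summarizes all AEs and all DDs, the latter by device type.

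Most of this stands. A reader might infer from 8.2.6 that DDs which caused minor harm drop out of the co-primary endpoint in general; the documents do not support that. A reader might also want to express the loss as a change in an event rate. That has no basis here: no DD rate is given, and section 9.2 makes the safety assessment descriptive, with no threshold or test that one case could alter.

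The reply does not answer the timing point, because the sponsor's review starts after the site's report. It also leaves open which scope governs when the sponsor's finding conflicts with 8.1.3. The remaining caution concerns flowchart 1, which section 8.3 says details the procedure. It is not shown in the text available, so it could not be checked whether it closes the gap.

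**Conclusion.** The point holds as an inconsistency between sections 8.1.3 and 8.2.6 on one side and section 8.2 on the other, and its main consequence is for reporting. For a DD that caused a non-serious AE but could have caused a serious one, the site's limit becomes 30 days instead of 24 hours. This assumes that the site follows 8.1.3 and 8.2.6 as written and that flowchart 1 does not say otherwise.

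The effect on the co-primary safety endpoint is narrow. It is confined to non-study implants, instruments and prosthetic parts, and there to cases that are not classed as ADEs and so depend on the sponsor's review alone. The number of such cases cannot be estimated from the documents and is probably small. The bone-level endpoint, its sample size and its power are not affected. The correction is worth making because the rule is explicit, concerns safety reporting and is easily put right.

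**What to change.** - In sections 8.1.3 and 8.2.6, delete the clause that restricts SADE potential to DDs without an AE or SAE, so that the site assesses every DD, as section 8.2 already requires of the sponsor.
- In section 8.3.2, state that the expedited route applies to every DD with SADE potential, whether or not it also caused a non-serious AE. Check flowchart 1 against this.
- In the safety analysis in section 9.2, count every such DD in the co-primary listing, with a cross-reference to any linked AE so that one occurrence is not counted twice.

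The cost is a few wording changes, a SADE-potential field in the eCRF that is open for all DDs, and slightly more assessment at the sites for a rare event.

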## 8.2.7 Expectedness (Anticipation)

For each ADE and AE's at or related to an implant position where a BLT Roxolid® implant was placed during surgery or there is a temporal relationship to a dental treatment procedure the sponsor (including at least one medical expert) will determine whether the event is anticipated (expected) or unanticipated (unexpected) based on knowledge of the reaction and any relevant product information as documented in the IfUs (Annex 1, Annex 2), the risk management report for implants (35) or in the list of potential expected AEs and ADEs in the current protocol (Table 5), without claim to completeness. The event will be classed as either:

- Expected the reaction is consistent with the effects of the device listed in the Risk Management Report, IFU or the list of potential expected AEs and ADEs in the current protocol (Table 5).
- Unexpected the reaction is not consistent with the effects listed in the Risk Management Report, IFU or the list of potential expected AEs and ADEs in the current protocol (Table 5).

An expected ADE can become an unexpected ADE, if there is a change in either the severity, outcome or occurrence of the ADE.

# Table 5: List of Potential Expected Adverse Events and Adverse Device Effects following dental implant treatment

Dental implant treatments involves implant placement and prosthetic restoration. The table includes AEs and ADEs expected for implant treatment in general and specifically for procedures related to the implant or abutment, without claim to completeness.

	gical complications	Implant	abutment
Gener		······	···•
•	Bruising	X	
•	local inflammation	X	X
•	Local irritation	X	X
•	Swelling	X	
•	Infection at implant site without suppuration (local)	X	X
•	Infection at implant site with suppuration (=peri-implant abscess, local)	Х	X
•	Gingival enlargement (=gingival hyperplasia, gingival hypertrophy, gum overgrowth, hypertrophic gingivitis)	X	
•	Gingival recession (=dehiscence of the gingiva, receding gums)	x	
•	Exfoliation (in connection with the dental implant)	X	
•	Pain	Х	
Hard t	issue related		
•	Low primary stability (at surgery)	X	
•	Implant mobility (tactile horizontal or vertical)	X	
•	Early loss/failure of implant (i.e. before osseointegration)	Х	X
•	Late loss/failure of implant (i.e. after osseointegration)	Х	X
•	Radiolucency	X	
•	Bone necrosis	Х	
•	Bone damage/ fracture	Х	X
•	Delayed healing/osseointegration	Х	
•	Excessive bone resorption/bone loss*	Х	
Syster	nic complications		
•	Asphyxiation	X	X
•	Anaphylaxis	Х	X
•	Slowed recovery after treatment	Х	
•	Implant obstructs patient airway	Х	
•	Allergic reaction/ hypersensitivity to implant material	Х	
•	Allergic reaction/ hypersensitivity to abutment material		X
•	Toxicity reaction	Х	X
•	Systemic infection	Х	X
Other	•	··········	
•	Foreign body sensation	X	
•	Oro-sinus or oro-nasal intrusion/fistula	Х	
•	Permanent paresthesia, dysesthesia	X	Ĭ
•	Chronic pain	X	
•	Nerve damage in the jaw	X	
Mechanical complications		Implant	abutment
•	Implant cannot be placed	X	
•	Loosening of abutment	х	X

Loosening of occlusional screw	Χ	X
Loss/ failure of prosthesis/ reconstruction		X
Loss/failure of an healing cap		X
Fracture/ breakage of abutment		X
Fracture of occlusional screw		X
Fracture of implant	X	

 
Fracture/ chipping of prosthesis / framework
 
	Х	X

 
Implant connection is damaged and non-restorable
 
	Х	

 
Abutment cannot be fixed properly on the implant
 
	X	X

 
Jamming of abutment
 
		X

 
Screw does not fit properly
 
	X	X
Stuck screw	X	X
Bridge does not fit	Х	X
The Crown does not fit		X
Coping or protective cap does not fit		X
Corrosion of the abutment		X
Irreversible damage to adjacent/opposing teeth or	X	
unfavorably affected adjacent teeth		

 
Loss of cement retention (of prosthesis)
 
		X
Other complications		abutment

 
Esthetic problem/poor aesthetic outcome
 
	X	X
Jaw fracture	X	
Phonetic difficulties	X	X
Aspiration of implant	X	

 
Swallowing of implant
 
	X	
Aspiration of abutment		X
Swallowing of abutment		X

 
Aspiration of component other than implant and abutment.
 
Specify component
 
		

 
Swallowing of component other than implant and abutment.
 
Specify component
 
		

 
Implant burned to mucous membrane (through MRI energy)
 
	Х	
	··· <del>†</del> ······	Χ

\* Based on the 1st European Workshop on Periodontology an average marginal bone loss (MBL) of less than 1.5 mm within the 1st year after the insertion of the prosthesis was specified as criteria for measuring success (43). Based on this information the central radiologist will flag any bone level changes greater than 1.5 mm between implant loading and the 12-months follow-up visit. The study manager will review the flagged values and discuss with the principal Investigator whether the bone level change will be reported as an ADE.

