#### 7.2.1 Randomization

Assignment of one study test (placement of SLActive® implant(s)) and one study control quadrant(s) (placement of SLA® implant(s)) (=study quadrants) will be based on randomization at surgery visit, before implant placement but after the preparation of the bed where the first implant will be placed.

If there are two quadrants (suitable for study required implant placement) available in the same arch, those two quadrants will be selected for randomization. If this is applicable for the upper and lower arch the study site can select the arch for randomized. The randomization will be "left/right" to assign test/control treatment).

If the two available quadrants (suitable for study required implant placement) are from different arches the randomization will be "upper/ lower" to assign test/control treatment.

[figure not shown]

Randomization of eligible subjects will be performed using an Electronic Data Capturing (EDC) system. After log into the EDC system and entering the suitable quadrants for study required implant placement the system determines the treatment allocation. In case it's not possible to access the EDC system at site the Contract Research Organization (Factory) can provide the randomization arm.

The randomization in the EDC is programmed by Data Management. A block randomization process will be applied to randomize each center separately. Additionally, the randomization will be stratified for randomization in the same arch or in different arches, therein 2 randomization lists will be produced.

Quadrant I-IV are defined as:

The randomization code is a five digit number, consisting of the center number (e.g. 1 or 2), the individual patient number (01, 02, 03,...) and the randomization list number (01, 02). No access to the master randomization list will be available to the study centers, the external Monitors, the subjects and the Straumann non-Clinical-Research project team.

The study control and study test implant will be defined as described in Section 3.3

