## 7.3.1.2 Mean Implant Bone Level Changes

On the standardized peri-apical radiographs mesial and distal implant bone levels will be evaluated. The reference point for the bone level measurement is the implant shoulder. The bone level will be measured as the distance between the implant shoulder and the first visible bone contact on the implant. The bone level will be measured on the mesial and distal aspect of the 2 study implants. Mean bone level changes between two time-points will be computed by subtracting the average bone level from one visit with the other.

In this study, the time point and number of X-rays do not differ from the standard daily practice used for implant patients outside this study.

Original, full X-ray and photographs need to be saved in patients files.

A shared server has been made available to the study site for upload following pseudonymization. Files should be saved in their original resolution, ideally in .tiff format. The X-ray should include neighboring teeth and the entire implant length and include the following information:

- Study ID (CR 2017-05)
- Patient ID
- Visit #
- Date of visit
- Study implant location (FDI)

Any additional information present on the original X-ray needs to be removed before upload onto the shared server.

A blinded expert will perform the bone level measurements on the X-rays according to the X-ray evaluation protocol. Measurements will take into account distortion based on changes on the radiograph from the true dimension of the implant.

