## Safety and tolerability analysis

The safety analysis will be performed on data collected as specified under 7.3.12 and 7.3.13

The analysis of safety assessments in this study will include summaries of the following of safety and tolerability data collected for each subject:

- Adverse events
- Serious adverse events
- Adverse device effects
- Device deficiencies
- Device deficiencies that could have led to a serious adverse device effect

Summaries of the incidence rates (frequencies and percentages), severity, outcome and relationship to the investigational device and or/ study procedures of individual AEs will be

prepared. AEs which concern an implant position where a BLT, Roxolid® implant was placed during surgery or AEs which are related to a treatment procedure at such a position will be summarized by study treatment and overall and the used products at this position will be listed.

DDs will be summarized per medical device type (implant type, abutment type, instruments).

To address the co-primary objective of this study "SLActive® implants are safe" a descriptive assessment of adverse device effects and device deficiencies that could have led to a serious adverse device effect will be made, this will include listings and tables by treatment, severity, relatedness and outcomes.

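### The plan sets no criterion, no masking and no full tabulation for deciding whether bone level changes flagged above 1.5 mm count as adverse device effects

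*Combined protocol and SAP*

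**What the plan says.** - **Endpoint.** Section 3.4.1 lists two primary parameters: bone level change, and "Occurrence of adverse device effects and device deficiencies that could have led to a serious adverse device effect".
- **Analysis.** For the co-primary safety objective, the safety paragraph of section 9.2 states that "a descriptive assessment of adverse device effects and device deficiencies that could have led to a serious adverse device effect will be made", with listings and tables by treatment. It sets no test, threshold or success rule.
- **Measurement.** Section 7.3.1.2: "A blinded expert will perform the bone level measurements on the X-rays".
- **Flag.** The Table 5 footnote says that "the central radiologist will flag any bone level changes greater than 1.5 mm between implant loading and the 12-months follow-up visit".
- **After the flag.** The same footnote has the study manager review the flagged values and "discuss with the principal Investigator whether the bone level change will be reported as an ADE".
- **General ADE rule.** Section 8.1.4: "Any AE which has even a possible relationship to the investigational device will be classified as an ADE".
- **Masking.** Section 3.1 calls the trial single-blinded. Section 7.2.2 masks the patient and separates the assessor from the operator. Section 7.2.1 keeps the master randomization list from the sites, the outside monitors, "the subjects and the Straumann non-Clinical-Research project team".

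**The concern.** The plan has an objective signal, a preset limit applied to masked radiograph readings, and then lets two people decide case by case whether it enters a co-primary endpoint. One of them belongs to the sponsor. The footnote does not say what should tip the decision, what the default is, whether the two people are masked to the surface, or where an unreported flag would appear.

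The safety co-primary has no threshold, so its value rests on the tables being complete. If flagged losses can drop out before they are tabulated, a reader cannot tell a surface with no large losses from one whose large losses were judged not reportable. The paired design makes this matter more, because any difference in handling between the two surfaces shows up directly as a treatment contrast.

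**Working it through.** **Reading the passages together**

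1. *Other events are handled more firmly.* Section 7.2.3 makes lack of primary stability reportable as an ADE without discussion. Low primary stability and excessive bone loss both stand in the hard-tissue block of Table 5. Section 8.2.2 requires a relationship assessment for every adverse event at a study implant position.
2. *The order is reversed.* Under section 8.2 the investigator assesses an event, the sponsor reviews that assessment in writing, and "In case of disagreement between the sponsor and the principal investigator(s), both opinions will be communicated to concerned parties". These safeguards attach to recorded adverse events. The footnote's discussion takes place before any record need exist.
3. *Timing weakens the usual route.* Section 6.10 places the 12-month radiograph at Visit 9, the last visit. Section 7.3.12 ends adverse event collection when the patient completes that visit. Central reading of an uploaded image will normally come later. An investigator may notice gross loss on the film, but the footnote is the only stated route for the measured flag.
4. *Masking of the two roles is not stated.* The sponsor's clinical research team is not among those denied the list (7.2.1), and article numbers are recorded at surgery (7.2.3).

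**Size**

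Inputs from section 9.4: SLActive 0.43 mm (SD 0.22), SLA 0.46 mm (SD 0.20), correlation 0, margin 0.10 mm, one-sided alpha 0.05, 51 pairs, 60 enrolled, 20% dropout. The limit of 1.5 mm is from the Table 5 footnote.

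*Check that the planning inputs are read as intended.* SD of the difference = sqrt(0.20² + 0.22²) = 0.297 mm. Distance to the margin = 0.10 + (0.46 − 0.43) = 0.13 mm. A one-sided paired t-test with 51 pairs (noncentral t) gives power of 92.4%, the plan's figure. The present point does not depend on it.

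*Weight of one flag.* There is one study implant of each surface per subject, so per surface one flag is one subject.
- Safety population if all 60 are treated: 1/60 = 1.7 points.
- Planned evaluable pairs: 1/51 = 2.0 points.
- After 20% dropout, 60 × 0.80 = 48: 1/48 = 2.1 points.

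*Flags expected under the planning values.*
- Normal shape: SLActive (1.5 − 0.43)/0.22 = 4.86 SD, tail about 6 × 10⁻⁷. SLA (1.5 − 0.46)/0.20 = 5.20 SD, tail about 1 × 10⁻⁷.
- Lognormal with the same mean and SD: tails of about 0.23% (SLActive) and 0.11% (SLA). Among 60 implants each this is 60 × 0.0023 = 0.14 and 60 × 0.0011 = 0.07 expected flags.

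*Flags under assumed rates.* The documents give no rate, so the range below is an assumption. Expected flags = 60p, and P(at least one) = 1 − (1 − p)^60, for 60 SLActive implants.

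| Assumed rate p | Expected flags | P(at least one) |
|---|---|---|
| 0.5% | 0.3 | 26% |
| 1% | 0.6 | 45% |
| 2% | 1.2 | 70% |
| 5% | 3.0 | 95% |

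*Illustration at the top of that range.* Three flags, all reported: 3/60 = 5.0% (exact 95% CI 1.0 to 13.9). The same three, none reported: 0/60 = 0% (0 to 6.0). This counts bone-loss ADEs only; other ADEs would add to both figures.

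**The case against.** The other side has a good deal. The limit and time window are fixed in advance and the reading is masked. The measured change stays in the bone level endpoint whatever happens to the ADE record. Section 9.1 requires minima and maxima by treatment and visit, so an extreme value should be visible. That is a partial safeguard: a maximum does not show how many implants passed the limit or how they were classified, the primary effectiveness analysis uses the per-protocol population (9.3), and outlier handling is left to the blind data review (9.1).

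Four stronger readings are tempting, and the documents do not support them.

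- *That a flag counts only if both parties agree.* The footnote says they discuss it. Neither is given a veto, the investigator can record adverse events independently (7.3.12), and section 8.2 provides for disagreement.
- *That the decision is made unblinded.* No passage says so of either role, and none says that the principal investigator is the operator. Section 7.2.1 also denies the list to the study centers. What can be said is that masking is not stated.
- *That the footnote contradicts section 8.1.4.* That rule applies once there is an adverse event. A radiographic flag is a measurement, and the footnote does not even give the direction of change, so asking first whether the value is an untoward event is compatible with the rule.
- *That the trial's formal conclusion is at risk.* The safety co-primary is descriptive, and the non-inferiority test on bone level does not use the ADE count.

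It is also fair that relationship assessment leaves judgement in place, since an investigator may still call an event unrelated. This is why tabulating all flags is the part of the fix that matters most.

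**Conclusion.** The point holds as a gap in ascertainment and reporting. The route from a flag to the co-primary ADE count has no criterion, no stated masking and no requirement to show flags that are not reported, and ordinary adverse event reporting is not a sure backstop at the last visit. The consequence is a descriptive count that may be incomplete, by 1.7 points per flag on 60 subjects or about 2 points on 48 to 51. Under the planning values few or no flags are expected; with assumed rates of 0.5% to 5%, the chance of at least one on the test surface runs from 26% to 95%. Type I error, power and the non-inferiority decision are untouched.

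This rests on 60 treated subjects with one study implant per surface, on the assumed range of flag rates, and on no other study document supplying the missing rule. Section 7.3.1.2 refers to an X-ray evaluation protocol that was not available here. The change is worth making because it is nearly free, not because the effect is large.

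**What to change.** 1. **Section 9.2, safety analysis.** Within the co-primary safety table, list and tabulate by surface every study implant flagged for bone loss above 1.5 mm between loading and 12 months, whatever its ADE classification. Say loss, so that the direction is clear.
2. **Table 5 footnote.** State that each flagged loss is recorded under the existing Table 5 bone-loss term and assessed for relationship under sections 8.2.2, 8.1.4 and 8.2: investigator assessment, sponsor review, both opinions documented. State that the assessment is made without reference to the surface where feasible.

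The cost is an edit to one footnote, one table and at most a few additional adverse event records. No visit, measurement or sample size changes.
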